8.3.3 Covariate Assessment

- Demographics
 - Age at BLINCYTO® initiation
 - Sex
- Line of therapy at BLINCYTO® initiation (primary refractory, first relapse, second relapse, third relapse, later relapses)
- ALL disease status at diagnosis
 - Bone marrow blast count
 - Cytogenetics and molecular subtypes (non-Philadelphia chromosome cytogenetic abnormalities)
 - Extramedullary disease

- ALL disease status at time of treatment with BLINCYTO®
 - Bone marrow blast count
 - Cytogenetics and molecular subtypes (non-Philadelphia chromosome cytogenetic abnormalities; including ABL1 kinase domain mutations)
 - T315I mutation
 - Extramedullary disease
- Number of previous TKI treatments
- Front-line treatments:
 - Regimens
 - Clinical trials
 - TKIs (Imatinib, Dasatinib, Nilotinib, Ponatinib) + chemotherapy
 - TKIs + corticosteroids
 - Duration of remission (ie, time from date of treatment response to date of relapse)
 - Response
- Treatment in relapsed cases (for patients in second or later relapse):
 - Regimens
 - Clinical trials
 - TKIs (Imatinib, Dasatinib, Nilotinib, Ponatinib) + chemotherapy
 - TKIs + corticosteroids
 - Duration of remission (ie, time from date of treatment response to date of relapse; for each occurrence of relapse)
 - Response
- Prior alloHSCT
- Time from alloHSCT to relapse
- Performance Status (ECOG or equivalent)
- For chemotherapy treatments in the frontline and relapse lines of therapy, the specific names of the regimen will be recorded if specified. The names of the individual drugs making up the regimen will also be recorded. In cases when the regimen name is not stated, the names of the individual chemotherapy drugs will be recorded.

8.3.4 Validity and Reliability

The data collected for this study will be derived from patient medical records and used to populate eCRFs with instructions for site investigators. Instructions will be provided to investigators regarding eCRF completion for accuracy of data extraction from medical records.

8.4 Data Sources

Patient-level data will be obtained by abstraction of data from existing medical records at participating study sites.

8.5 Study Size

The actual number of patients that will be included in the study will be dependent on the clinical use of BLINCYTO® at participating sites. We aim to collect data on approximately 15 to 30 patients initiating BLINCYTO® treatment for Ph+ R/R B-cell precursor ALL after commercial availability of BLINCYTO® in China, see Study Design Schema. The rationale for this sample size is based on the incidence of Ph+ status, constituting only about a quarter of B-cell precursor ALL patients, hence a relatively small number of cases can be recruited given that B-cell precursor ALL is a relatively rare disease. Additionally, the prior global clinical trial (Study 20120216; [Martinelli, 2017]) for the treatment of Ph+ R/R B-cell precursor ALL with BLINCYTO® studied 45 patients across sites in Europe and the US and we would expect smaller numbers over the planned study period in China. Further, 15 to 30 patients is a plausible estimate for an initial experience based on the expected clinical use of BLINCYTO® in China since being available in the country.

8.6 Data Management

8.6.1 Obtaining Data Files

Data are abstracted by the investigator, site staff, or delegates from medical records into an electronic data capture (EDC) system provided by Amgen. The EDC system will include eCRFs designed to capture the variables and outcomes of interest. Updates to the eCRFs will be automatically documented through the software's "audit trail".

The sponsor, or designated vendor, will provide protocol-specific training and eCRF completion instructions in advance of the study data collection period to ensure clarity on the questions and accuracy of the data to be captured.

The data collected for this study will be derived from medical records that are kept per routine clinical practice for the documentation and decision-making of a patient's care. The investigator must maintain accurate documentation that support the information entered into the eCRF. All source documentation supporting entries into the eCRFs must be maintained and available upon request.

Amgen representative(s) and regulatory authority inspectors are responsible for contacting and visiting the investigator for the purpose of inspecting the facilities and,

upon request, inspecting the various records of the clinical study (eg, CRFs and other pertinent data) ensuring patient confidentiality is respected.

8.6.2 Linking Data Files

Not applicable.

8.6.3 Review and Verification of Data Quality

Data entered into the EDC system is reviewed to ensure accuracy and quality. Upon entry into the eCRF, data are reviewed for outliers, inconsistent, invalid, or missing data and any other apparent discrepancies as outlined in the data management plan. In the event clarification on any data is required, queries are created in the EDC system for site resolution.

A clinical monitor or designee will verify the eCRFs at regular intervals throughout the study to confirm that data entered into the eCRF are accurate, complete, and verifiable from medical records.

The investigator is responsible for verifying all data entries and query responses are accurate and correct by electronically signing the eCRF.

8.7 Data Analysis

8.7.1 Planned Analyses

Retrospective data will be collected at one point in time and analyzed.

8.7.1.1 Primary Analysis

Primary objectives of this study are descriptive in nature which are to measure CR/CRh rate and EOI. These two objectives are reported by proportion and 95% confidence interval (CI). The secondary objectives are describing treatment patterns, which will be described by median and IQR. Further secondary objectives alloHSCT, MRD rate, OS, and RFS will be described as proportions. The analysis will be conducted at the end of the study data being collected as a single final analysis set.

8.7.2 Planned Method of Analysis

8.7.2.1 General Considerations

Analyses will be descriptive in nature. Demographic and patient characteristics will be summarized by descriptive statistics. Continuous variables will be summarized by n, mean, standard deviation, median, Q1 (25th percentile), Q3 (75th percentile), and ranges. Categorical variables will be summarized by counts and percentages for each category. Proportion and 95% CIs will be reported for patients with CR/CRh, MRD negative status, and alloHSCT.

For time-to-event outcomes, the Kaplan-Meier (K-M) method will be used to estimate the 6-month OS probability, including survival rates at selected timepoints (eg, 3- or 6-month, 12-month). The two-sided 95% CIs for proportion, median (if reached) and other quantiles of survival estimates will be constructed with using Brookmeyer method (Brookmeyer and Crowley, 1982), whereas the 95% CIs for survival rates at landmark timepoints will be calculated based on Greenwood's formula (Greenwood, 1926). The median of follow up time will be provided in addition and estimated by reverse K-M method (Schemper and Smith, 1996). K-M curves will also be presented.

8.7.2.2 Missing or Incomplete Data and Lost to Follow-up

Attempts to collect missing data and incomplete data will be resolved by using the patient medical records and through site queries. The eCRFs will be designed to minimize missing data and to optimize the integrity of collected data. Patients' records will not be excluded because of missing data but will be recorded for as missing if a specific covariate is not available for evaluation. The proportion of missing data will be reported for each measured variable in the study. Since data is collected from medical charts led as per standard of care, it is expected that data will be reasonably complete, however some missing data can also be expected.

8.7.2.3 Descriptive Analysis

8.7.2.3.1 Description of Study Enrollment

Medical records of patients treated with BLINCYTO® for Ph+ R/R B-cell precursor ALL at participating clinical centers in China will be eligible for inclusion. The eligibility criteria are given in Section 8.2.3. The enrollment period will be approximately 6 months from FSE on the study.

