6.4 Statistical Inference (Estimation or Hypothesis[es])

There is no formal hypothesis to be tested. The study is descriptive in nature and will assess effectiveness and safety outcomes.

7. Research Question and Objectives

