8.2.1 Study Period

BLINCYTO® was approved in for use in China on December 2, 2020. The eligible treatment with BLINCYTO® should occur after December 2, 2020. Data abstraction of eligible medical records retrospectively will occur at a minimum of 6 months after first infusion of BLINCYTO® treatment for each patient. Data collection will occur at one point in time. The enrollment period will be approximately 6 months from first patient enrolled (FSE) on the study.

End of Study (EOS) is defined as the last chart abstraction for the last patient enrolled.

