8.2.3 Subject/Patient/Healthcare Professional Eligibility

8.2.3.1 Inclusion Criteria

- Adult patients (≥ 18 years at the initiation of BLINCYTO®) with Ph+ R/R B-Cell precursor ALL confirmed by either cytogenetics or molecular test
- Patients initiated BLINCYTO® at least 6 months prior to data abstraction
- Informed consent provided if required per local regulations

Note: Patients treated with TKIs in combination with BLINCYTO® are eligible.

Deceased patients at the time of data abstraction are eligible. An informed consent form (ICF), if required per local regulation needs to be signed on the day of enrollment and is required before chart abstractions can begin. Medical records of patients participating in clinical trials will be included up to the time the patient enrolls into a clinical trial, however patient data after enrollment in a clinical trial will not be collected.

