8.9.2 External Validity of Study Design

The patient population will come from sites that have agreed to participate in this study and thus the results may not be generalizable to all sites in the People's Republic of China. Additionally, patients that have agreed to participate in this study may be different from the patients not consenting to participate.

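### Charts enter the study after outcomes have usually occurred, and no rule makes sites list and enter every eligible patient or count those left out

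*Protocol*

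**What the plan says.** - **Entry.** Section 8.7.2.3.1: "Medical records of patients treated with BLINCYTO® for Ph+ R/R B-cell precursor ALL at participating clinical centers in China will be eligible for inclusion". It refers to section 8.2.3 for the criteria, which state who qualifies but not that all who qualify are entered.
- **Timing.** Section 8.2.1: "Data abstraction of eligible medical records retrospectively will occur at a minimum of 6 months after first infusion". Each chart is abstracted once.
- **Size.** Section 8.5: "We aim to collect data on approximately 15 to 30 patients initiating BLINCYTO® treatment for Ph+ R/R B-cell precursor ALL", and "The actual number of patients that will be included in the study will be dependent on the clinical use of BLINCYTO® at participating sites". Section 8.2.2 expects 7 sites. No cap or quota per site is set.
- **Consent.** Where local rules require it, the form "needs to be signed on the day of enrollment and is required before chart abstractions can begin" (section 8.2.3.1). Section 9.1 makes consent for deceased patients conditional on local law. Section 8.9.2 concedes that "patients that have agreed to participate in this study may be different from the patients not consenting to participate".
- **Analysis set.** The full analysis set in section 8.7.2.4 takes infused patients who are in the study and meet the criteria, so it begins after entry.
- **Safeguards.** Deceased patients are eligible (8.2.3.1), and the sites have confirmed that they can collect their data (8.2.2). Charts are not dropped for missing data (8.7.2.2). Patients with no response assessment count as non-responders (8.7.2.4).
- **Selection bias.** Section 8.9.1.3 covers the type of centre and differences in laboratory methods. Checklist item 4.3 in Appendix B answers yes, citing section 8.2, to whether sampling from the source population is defined.

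**The concern.** In a retrospective chart study, what protects against outcome-dependent entry is a rule fixing which charts go in before anyone looks at how the patient fared. Sections 8.2, 8.5 and 8.7.2.3.1 contain no such rule: no requirement for all or consecutive eligible patients, no source list, no order of entry and no tally of eligible patients left out. Section 8.2 gives eligibility, sites and timing, so the checklist answer on sampling has nothing behind it.

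If entry is related to response or survival, CR/CRh and 6-month OS describe the patients who were entered rather than those who were treated. Without a denominator, a reader cannot tell how far apart the two are. Section 12 sends the results to the Chinese regulator and to publication. This is a protocol matter, because no later analysis can recover patients who were never listed.

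**Working it through.** **1. The plan's own figures.** Section 6.4 states "There is no formal hypothesis to be tested", and the 15 to 30 patients rest on feasibility, so there is no power or precision figure to reproduce. The benchmark in section 6.2 does reproduce: 35.6% of 45 is 16 responders, and exact Clopper-Pearson for 16/45 gives 21.9% to 51.2%. The lower limit matches the protocol.

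**2. Have outcomes occurred before entry?** Section 6.3 gives a typical course as a median of 2 cycles at 28 days per cycle, that is 2 × 28 = 56 days of cycle time. Abstraction comes at 6 months or later. Two-cycle response and the 6-month OS landmark therefore usually lie in the past, although section 8.9.1.2 expects some outcomes to be missing.

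**3. Omitted charts, in counts.** Responder numbers are set near the benchmark rate.

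| Eligible | Responders | Non-responders omitted | True | Observed | Shift |
|---|---|---|---|---|---|
| 15 | 5 | 2 | 33.3% | 5/13 = 38.5% | +5.1 |
| 15 | 5 | 3 | 33.3% | 5/12 = 41.7% | +8.3 |
| 30 | 11 | 3 | 36.7% | 11/27 = 40.7% | +4.1 |
| 30 | 11 | 5 | 36.7% | 11/25 = 44.0% | +7.3 |

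**4. Omitted charts, in rates.** Let p be the true rate, a the share of responders (or survivors) entered and b the share of non-responders (or deceased) entered. The expected observed rate is p·a / [p·a + (1 − p)·b]. The documents give no entry shares and no 6-month OS, so a, b and the OS values are assumptions.

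CR/CRh at p = 0.356:
- a = 1, b = 0.8: 0.356/0.8712 = 40.9% (+5.3 points)
- a = 1, b = 0.6: 0.356/0.7424 = 48.0% (+12.4)
- a = 0.8, b = 1: 0.2848/0.9288 = 30.7% (−4.9)
- a = 0.6, b = 1: 0.2136/0.8576 = 24.9% (−10.7)

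6-month OS at an assumed p = 0.55:
- a = 0.9, b = 0.7: 0.495/0.810 = 61.1% (+6.1)
- a = 0.9, b = 0.5: 0.495/0.720 = 68.8% (+13.8)
- a = 0.7, b = 0.9: 0.385/0.790 = 48.7% (−6.3)

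The downward cases are realistic where living patients can refuse consent but the deceased need none. The upward cases fit easier entry of patients who did well.

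**5. What the planned intervals cover.** Clopper-Pearson gives 11.8% to 61.6% for 5/15 and 19.9% to 56.1% for 11/30. These limits, and Greenwood limits for OS, express sampling error among the patients entered. They contain no term for a or b.

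**6. What a roster would add.** If every eligible chart is entered, a = b = 1 and the shift is zero. If some listed patients stay out, the rate can be bounded by counting them all as non-responders, then all as responders:
- 15 entered (5 responders), 3 not entered: 5/18 to 8/18, or 27.8% to 44.4%
- 15 entered (5 responders), 5 not entered: 5/20 to 10/20, or 25.0% to 50.0%
- 30 entered (11 responders), 6 not entered: 11/36 to 17/36, or 30.6% to 47.2%

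**The case against.** The strongest reply is that the protocol nowhere lets sites choose. Section 8.5 ties the number included to clinical use at the sites, which reads more like taking everyone than selecting; there is no quota, and section 6.3 treats 15 as a minimum. A reader might divide 15 to 30 by 7 sites, get 2.1 to 4.3 charts each, and infer that sites have charts to spare. The documents do not support that. They give no count of eligible charts per site and justify the size by scarcity. The US retrospective study in section 6.3 found 55 relapsed or refractory Ph+ patients at 11 institutions, or 5 each, so 2 to 4 may be nearly everyone. This part of the reply stands: room to choose is not shown, and the point rests on the absence of a rule.

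A reader might also infer that any bias must flatter the drug. It need not; the working shows shifts both ways.

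The safeguards for deceased patients and incomplete charts are real and narrow the problem, but they do not settle who is entered. The consent concession in section 8.9.2 names one route without counting it. The intervals are already wide, with half-widths of about 25 points at 5/15 and 18 at 11/30, so most shifts above lie inside them. That limits the practical weight. It does not make a systematic shift visible or show its direction.

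**Conclusion.** The point holds as a gap in the design: entry follows the outcomes, and no provision requires complete entry or a count of omissions. Under assumed entry shares of 50% to 100%, the primary CR/CRh rate or 6-month OS could shift by roughly 5 to 15 points, up or down, outside what the planned intervals express. The count examples (36.7% to 44.0%, 33.3% to 41.7%) need only three to five omitted charts. These sizes are illustrations of what the plan would not detect. The documents contain no evidence that selective entry will happen. It would also go too far to say that a roster disposes of the problem: it removes selection by choice only if paired with a duty to enter every eligible patient, and consent refusals remain. The change should be made before abstraction starts.

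**What to change.** 1. In section 8.2, require each site to list from pharmacy or dispensing records all patients who started BLINCYTO for Ph+ R/R B-cell precursor ALL since 2 December 2020, and to enter every eligible one regardless of outcome.
2. Report the numbers listed, eligible, entered and not entered, with the reason for non-entry and, where local rules permit, vital status. Where patients remain unentered, give the simple bounds shown in the working.
3. Extend section 8.9.1.3 to selection of charts within a site, and bring the answer to checklist item 4.3 into line with the new text.

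The cost is protocol wording, modest site time for the list, and local permission for a de-identified log of patients not entered; where consent is required before abstraction, vital status of non-consenters may not be available. The documents give no cost figure, but section 8.8 already names pharmacy records as source documents and only about 7 sites are involved. Where consent is required and refused, the list counts and bounds the loss without removing it.

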8.7.2.3.2 Description of Subject/Patient Characteristics

Patient's demographic and clinical characteristics will be summarized using descriptive statistics. Refer to Section 8.3.3 for description.

8.7.2.4 Analysis of the Primary, Secondary, and Exploratory Endpoint(s) Analysis Set

Unless otherwise specified, all efficacy and safety analyses will be performed on the full analysis set (FAS), which will include all patients who received any infusion of BLINCYTO® in the study and met the inclusion/exclusion criteria.

General Principles

Analyses will be descriptive in nature. Demographic and patient characteristics will be summarized by descriptive statistics. Continuous variables will be summarized by n, mean, standard deviation, median, Q1 (25th percentile), Q3 (75th percentile), and ranges. Categorical variables will be summarized by counts and percentages for each category. Proportion and 95% CIs will be reported for patients with CR/CRh, MRD negative status, and alloHSCT.

For time-to-event outcomes, the Kaplan-Meier (K-M) method will be used to estimate the 6-month OS probability, including survival rates at selected timepoints (eg, 3- or 6-month, 12-month). The two-sided 95% CIs for proportion, median (if reached) and other quantiles of survival estimates will be constructed with using Brookmeyer method (Brookmeyer and Crowley, 1982), whereas the 95% CIs for survival rates at landmark timepoints will be calculated based on Greenwood's formula (Greenwood, 1926). The median of follow up time will be provided in addition and estimated by reverse K-M method (Schemper and Smith, 1996). K-M curves will also be presented.

Primary Analyses

- CR/CRh rate:

The best response within the first two cycles of BLINCYTO® treatment will be used to estimate the percentages of patients with CR/CRh. Patients without response assessment within two cycles of treatment will be considered as non-responders. The proportion of CR/CRh and its corresponding Clopper-Pearson 95% confidence intervals (CI) will be estimated.

- Incidence of adverse EOI

The patient incidence of adverse EOI (recorded within 6 months of first infusion of BLINCYTO®) will be summarized by categories (ie, cytokine release syndrome, BLINCYTO® associated neurological adverse event, or infection) and preferred term in descending order of frequency.

Secondary Analyses

- The duration of infusion (in days) and cumulative dose (in µg) of BLINCYTO® will be tabulated as continuous variable for each cycle and the whole infusion period. The number of cycles started and completed will be summarized descriptively. Reasons for treatment interruptions may also be provided per each reason when

applicable. The number (percentage) of patients with BLINCYTO® monotherapy or concomitant therapy with TKIs will be summarized.

- The proportion and Clopper-Pearson 95% CI of patients who undergo alloHSCT will be estimated after BLINCYTO® treatment. Additional summary by best treatment response status will be provided.
- MRD status will be summarized descriptively by each category. The proportion and Clopper-Pearson 95% CI of MRD negativity will be estimated.
- OS will be estimated by K-M method, with patients censored on the last documented visit/assessment/contact date from the charter review if not dead. Landmark survival rates with associated 95% CIs at 3- and 6-months after first infusion of BLINCYTO® will be provided if estimable.
- RFS will be estimated by K-M method and only for patients who achieved CR/CRh within two cycles of BLINCYTO®. Patients with no documented relapse or death will be censored at the latest date indicating the subject remains in CR/CRh.

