Further consideration for feasibility of enrollment of Ph+ patients can be drawn from two additional real-world evidence studies. Study 20150136 is a post marketing commitment real-world study of BLINCYTO® safety and effectiveness, utilization, and treatment practices in routine clinical practice in countries in Europe. The study objectives were to characterize the safety profile of BLINCYTO® by characterizing adverse events, and to estimate the frequency and type of medication errors identified in patient charts. The latest interim analysis reported 144 Ph- R/R patients and 10 Ph+ R/R patients. Further reference is made to a non-Amgen sponsored study conducted to assess BLINCYTO® in a retrospective multicenter study at 11 academic institutions in the United States (Badar, 2020). The study enrolled B-cell ALL patients age ≥ 18 years at the time of BLINCYTO® administration, and who received drug outside of clinical trials. Medical records were reviewed to collect demographic, patient-related, disease related and clinical outcome data. These patients were evaluated for response, RFS, OS from the time of BLINCYTO® initiation, and toxicities. The study analyzed the data of 239 ALL patients. Overall, 61 (25%) with Ph+ were enrolled, of which 55 were diagnosed with R/R Ph+ B-cell ALL and received BLINCYTO®. Among the Ph+ patients, 29 patients received BLINCYTO® in combination with a TKI. Typical duration of treatment from the global perspective with BLINCYTO® has been a median of 2 cycles, 28 days/cycle.

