7.1 Primary

- To estimate the percentage of patients with CR/CRh within two cycles of treatment with BLINCYTO® in Chinese adults with Ph+ R/R B-cell precursor ALL
- To estimate the incidence of adverse EOI (recorded within 6 months of first infusion of BLINCYTO®)

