8.3.2 Outcome Assessment

Primary Outcomes

- CR/CRh rate within two cycles of BLINCYTO®. CR is defined as: < 5% bone marrow (BM) blasts, no evidence of extramedullary disease (EMD) and full recovery of peripheral blood counts defined as, platelets $\geq 100\,000/\mu\text{L}$, and absolute neutrophil count (ANC) $\geq 1000/\mu\text{L}$; CRh is defined as a CR with partial recovery of peripheral blood counts defined as platelets $> 50\,000/\mu\text{L}$ and $< 100\,000/\mu\text{L}$ and ANC $> 500/\mu\text{L}$ and $< 1000/\mu\text{L}$.
- Incidence of Adverse EOI. EOI are defined as: Cytokine release syndrome (CRS), BLINCYTO® associated neurological adverse event, and infection.

Secondary Outcomes

- BLINCYTO® use will be defined by BLINCYTO® treatment measured by number of cycles and duration of cycles. BLINCYTO® monotherapy and concomitant therapy with TKIs will be described.
- Occurrence of alloHSCT after BLINCYTO® treatment
- MRD status by flow cytometry or Polymerase Chain Reaction (PCR) within two cycles. MRD negativity is defined as: $<10^{-4}$ leukemic cells.
- OS is defined as the time from first infusion of BLINCYTO® until death due to any cause.
- RFS is defined for subjects who achieved CR/CRh within two cycles, as the time from first onset of CR/CRh until date of first documented relapse, or death due to any cause, whichever occurs first.

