10.1 Definition of Reportable Events

10.1.1 Adverse Events

An adverse event is any untoward medical occurrence in a subject/patient administered a pharmaceutical product(s) irrespective of a causal relationship with this treatment.

An adverse event can therefore be any unfavorable and unintended sign (including an abnormal laboratory finding, for example), symptom, or disease temporally associated with the use of a product(s), whether or not considered related to the product(s). The definition of an adverse event includes:

- Worsening of a pre-existing condition or underlying disease
- Events associated with the discontinuation of the use of a product(s), (eg, appearance of new symptoms)

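### The 6-month count of adverse events of interest does not separate events after transplant or next therapy; a cut summary and a stated exact CI would be cheap to add

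*Protocol*

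**What the plan says.** The window is part of the objective itself. Section 7.1 reads: "To estimate the incidence of adverse EOI (recorded within 6 months of first infusion of BLINCYTO". The operative analysis in Section 8.7.2.4 repeats it: "The patient incidence of adverse EOI (recorded within 6 months of first infusion of BLINCYTO®) will be summarized by categories", with a further breakdown by preferred term. Section 8.7.3 refers all safety analysis back to that text.

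Section 8.3.2 sets the categories: "EOI are defined as: Cytokine release syndrome (CRS), BLINCYTO® associated neurological adverse event, and infection". Only the neurological category is tied to the drug by name, and Section 10.1.1 defines an adverse event "irrespective of a causal relationship with this treatment".

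On exposure, Section 6.3 says that typical treatment worldwide "has been a median of 2 cycles, 28 days/cycle".

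On precision, Section 8.7.1.1 says of CR/CRh and EOI: "These two objectives are reported by proportion and 95% confidence interval (CI". Section 8.7.2.4 says: "Proportion and 95% CIs will be reported for patients with CR/CRh, MRD negative status, and alloHSCT". For the other primary endpoint it names the method: "The proportion of CR/CRh and its corresponding Clopper-Pearson 95% confidence intervals (CI) will be estimated". Its EOI bullet mentions neither an interval nor a method.

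**The concern.** The study is titled and reported as a description of BLINCYTO's effectiveness and safety, and Section 12 says that it will go to the Chinese regulator. Its EOI figure will be read as the toxicity of BLINCYTO. A patient with typical exposure spends most of the six months off the infusion. In that time the patient may proceed to alloHSCT, which Section 6.1 presents as the step that a second remission makes possible and Section 6.2 describes as carrying substantial morbidity and mortality, or may start other salvage therapy. An infection arising then counts the same as one arising during cycle 1. Responders who reach transplant could therefore raise the apparent toxicity of the drug that got them there.

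The data are abstracted once per patient (Section 8.2.1). A date that is not on the form at that point would mean reopening the charts.

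A smaller matter concerns the same endpoint. With 15 to 30 patients, an EOI percentage means little without its interval, and the section that specifies the analysis does not repeat that one is due.

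**Working it through.** **1. Is there any cut?** Sections 7.1 and 8.7.2.4 end the count at six months from first infusion. Sections 4 and 8.2.3.1 add one data rule: nothing is collected after a patient enters a clinical trial. No section ends or splits the EOI count at alloHSCT or at the start of other therapy.

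**2. How much of the window follows BLINCYTO?** Inputs: 2 cycles of 28 days (Section 6.3) and a window of 365.25/2 = 182.6 days. The protocol gives no interval between cycles, so a gap of 0 to 28 days is assumed. Share after cycle 2 = 1 - (56 + gap)/182.6.

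- Gap 0: 1 - 56/182.6 = 69%
- Gap 14: 1 - 70/182.6 = 62%
- Gap 28: 1 - 84/182.6 = 54%

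This describes a patient with the median number of cycles; those with more cycles have a smaller share.

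**3. Which categories are exposed?** For CRS, Appendix C admits fever, hypotension and hypoxia only when nothing else explains them. That narrows CRS but does not rule out CRS caused by a later therapy. For infection, Appendix C refers to CTCAE version 5.0 and sets no attribution limit. The neurological category is already restricted to BLINCYTO. The issue is chiefly infection.

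**4. Do the listed variables allow separation?** Infusion duration per cycle and alloHSCT after BLINCYTO are to be summarised (Section 8.7.2.4), so a split at transplant is feasible if the dates are captured. The treatment history in Section 8.3.3 covers front-line and earlier relapse therapy. The start of a new non-transplant therapy after BLINCYTO is not listed.

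**5. How large could the effect be?** The protocol gives no rate for infection, alloHSCT or next therapy, so no figure can be derived from it. As an illustration only, let p0 be the incidence before later therapy, q the share starting later therapy within the window, and r the chance of an event afterwards. The uncut incidence is p0 + (1 - p0) × q × r. With assumed ranges p0 = 10-40%, q = 20-40% and r = 30-60%:

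- Smallest excess: 0.60 × 0.20 × 0.30 = 3.6 points (0.5 patients of 15; 1.1 of 30)
- Largest excess: 0.90 × 0.40 × 0.60 = 21.6 points (3.2 patients of 15; 6.5 of 30)

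**6. The interval.** Section 6.2 cites 35.6% of 45 patients with a lower 95% bound of 21.9%. Taking the implied 16/45, Clopper-Pearson gives 21.9% to 51.2%. This reproduces the cited bound (Wald gives 21.6%, Wilson 23.2%), so the exact method agrees with the cited trial as well as with the CR/CRh analysis here.

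For zero events the exact upper limit is 1 - 0.025^(1/n):

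- 0/15: 1 - 0.025^(1/15) = 21.8%
- 0/30: 1 - 0.025^(1/30) = 11.6%

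At an illustrative 40%, 6/15 gives 16.3-67.7% and 12/30 gives 22.7-59.4%.

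**The case against.** The strongest reply is that the protocol says exactly what it estimates: all events recorded in a fixed window, without a causality judgement. For a single-arm chart review with no hypothesis, that is a legitimate descriptive measure. It avoids deciding attribution from retrospective notes and does not lose late events. This stands, and it is why the 6-month count should not be replaced. A cut at some number of days after the last infusion would be a debatable trade-off with no basis in the document.

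Several stronger readings are tempting and do not hold.

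- A reader might infer that CRS and infection are both counted regardless of cause. Appendix C does not support that for CRS.
- A reader might infer that all later treatment is swept in. Data after trial entry are not collected, and Section 6.1 notes that trial participation is strongly encouraged in this setting in China.
- A reader might infer that the EOI interval has been dropped. Section 8.7.1.1 is current text and still requires it; the list in Section 8.7.2.4 is not worded as exclusive.
- A reader might infer that the mixing could never be undone. alloHSCT is itself an outcome, and the eCRF and any SAP are not shown; only non-transplant next therapy is absent from the listed variables.

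It is also fair that Section 6.2 describes alloHSCT as open only to some patients, and that its timing is not given. A SAP could add the supplementary table, but it could not supply a date that was never abstracted.

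**Conclusion.** The point holds as a cheap improvement to one of the two primary endpoints. As written, the EOI count combines events on BLINCYTO with events, chiefly infections, that follow routine alloHSCT or non-trial next therapy, and the plan provides no summary that tells them apart. For a patient with the median exposure, roughly 54-69% of the window follows cycle 2, assuming a gap of 0-28 days between cycles. The resulting excess cannot be computed from the protocol. The 3.6 to 21.6 points shown above rest wholly on assumed rates and should not be quoted as an estimate of bias.

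The interval is a matter of reconciling two sections: Section 8.7.1.1 requires a 95% CI for EOI, and Section 8.7.2.4 neither repeats it nor names the method.

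**What to change.** 1. Keep the 6-month count as the primary EOI summary, as defined in Section 7.1.
2. In Section 8.7.2.4, add a second EOI summary by onset date, running from first infusion and stopping at the earlier of alloHSCT (start of conditioning) or the start of new anti-leukaemic therapy, within the same six months.
3. Add to the listed variables the start date and type of the next anti-leukaemic therapy, and the alloHSCT date if it is not already captured. Do this before abstraction begins, because each chart is read once.
4. In Section 8.7.2.4, state a Clopper-Pearson 95% CI for each EOI category, so that it agrees with Section 8.7.1.1.

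The cost is one extra table, one or two eCRF fields and a few sentences. The cut summary omits later events, but these remain visible in the 6-month count beside it.
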